7.4.3.3 Hb change from BL to each post-dosing time point

Hb value and change from BL Hb to each post dosing time point will be described by treatment arm on the FAS.

The analysis and SAS procedure will be the same as in Section [7.4.2.1](#)

7.4.3.4 Hb change from BL to the average Hb value of weeks 28 to 36, 44 to 52, and 96 to 104 regardless of the use of rescue therapy

The analysis will be done similarly as in Section [7.4.2.1](#) on the FAS except that it will be for weeks 28-36, 44-52 and 96-104.

7.4.3.5 Categorical analysis for Hb values

Proportion of Hb values :

The proportion of Hb values within 10-12 g/dL or ≥ 10 g/dL is a quantitative variable in the 0 – 100 range for each subject. Descriptive statistics for this variable will be presented by treatment arm. This variable will be presented in weeks 28-36, in weeks 44-52 and in weeks 96 -104, on the FAS.

Percentage of time during the Efficacy Emergent Period:

Descriptive statistics for the percentage of time with Hb values falling in each interval interval (<10.0 g/dL, within 10.0-12.0 g/dL, > 12.0 g/dL, ≥ 10.0 g/dL, > 13.0 g/dL and > 14.0 g/dL) between the first and last Hb assesment during the Efficacy Emergent Period will be presented by treatment arm.

The number and percentage of subjects, and the number of events, will be reported based on Hb values from the central lab with Hb increase by >2.0 g/dL between any two visits within 4 weeks of treatment.

Time to first occurrence of potential EH will also be analyzed similarly as in Section [7.4.2.7](#) (except that all data during the Efficacy Emergent Period will be taken into account for the analysis). The results will be presented by period (First 6 weeks, Week 7 - Week 27, Week 28 - Week 52 and > Week 52)

7.4.3.6 Occurrence (number) of hospitalizations,number of days of hospitalization per PEY and time to first hospitalization

The number and percentage of subjects with hospitalization will be reported. Descriptive statistics and frequency tabulations by treatment arm of the total duration of hospitalization (days), the average duration of each hospitalization (days), the number of hospitalizations, number of days of hospitalization per PEY and reason for hospitalization will also be reported.

Time to first hospitalization will also be analyzed similarly as in Section [7.4.2.7](#) (except that all data during the Efficacy Emergent Period will be taken into account for the analysis).

Superiority will be declared if the upper bound of the two-sided 95% confidence interval of the hazard ratio of the two treatment arms is below 1. Both descriptive summary and time to first hospitalization will be reported by eGFR category (<15 vs ≥15).

As a sensitivity analysis, the above analysis will be repeated using IPCW method (Appendix 10.7).

The analysis will be done on the FAS.

7.4.3.7 Occurrence and time to first use of rescue therapy during the First 24 Weeks [composite of RBC transfusions, IV iron supplementation and rescue ESA]

The number and percentage of subjects with rescue therapy during the first 24 weeks will be reported by treatment arm.

Time to first use of rescue therapy will also be analyzed similarly as in Section 7.4.2.7 (except that all data during the Efficacy Emergent Period will be taken into account for the analysis).

The analysis will be done on the FAS.

Superiority will be declared if the upper bound of the two-sided 95% confidence interval of the hazard ratio of the two treatment arms is below 1.

7.4.3.8 Occurrence and time to first use of RBC transfusions, number of RBC packs per subject, volume of RBC transfused per subject

The number and percentage of subjects with RBC transfusion will be reported. Descriptive statistics by treatment arm for number of RBC packs and volume of blood transfused will be reported. Time to first use of RBC transfusion will be analyzed during the Efficacy Emergent Period similarly as in Section 7.4.2.7

Mean monthly number of RBC packs and volume of RBC transfused during the Efficacy Emergent Period will be compared by treatment arm using a ANCOVA model as in Section 7.4.1.2.1 (except that no multiple imputation will be performed). Subjects with no medication record of RBC will be assumed that they received no RBC and therefore number of packs and volume will be set to 0. The number and percentage of subjects with number of RBC Packs/Volume >0 will be presented. The analysis will be done on the FAS.

Superiority will be declared if the upper bound of the two-sided 95% confidence interval of the hazard ratio of the two treatment arms is below 1.

7.4.3.9 Occurrence and time to first use of IV iron supplementation. Mean monthly IV iron (mg) per subject during day 1 to week 36, weeks 37-52 and weeks 53-104 (monthly defined as a period of 4 weeks)

The number and percentage of subjects who received IV Iron and the total amount of IV Iron used during the Efficacy Emergent Period will be reported descriptively by treatment arm.

The incidence and cumulative incidence of subjects receiving IV Iron will be calculated similarly as in Section 7.4.2.7

Mean monthly IV iron (mg) per subject during day 1 to week 36, weeks 37-52 and weeks 53-104 will be summarized by treatment arm. Subjects with no medication record of IV Iron will be assumed that they received no IV Iron (for patients under treatment during that month).

The analysis will be done on the FAS.

Furthermore, the total amount of IV Iron used during the efficacy emergent period as well as for Day 1 to week 36, weeks 37 to 52 and weeks 53 to 104.

Time to first use of IV iron will also be analyzed similarly as in Section 7.4.2.7

Superiority will be declared if the upper bound of the two-sided 95% confidence interval of the hazard ratio of the two treatment arms is below 1.

7.4.3.10 Occurrence and time to first use of ESA. Number of ESA-Week per year

The number and percentage of subjects with ESA use as rescue therapy, and the number of ESA-weeks/year will be reported descriptively by treatment arm.

Time to first use of ESA will also be analyzed similarly as in Section 7.4.2.7 (except that all data during the Efficacy Emergent Period will be taken into account for the analysis).

The analysis will be done on the FAS.

Superiority will be declared if the upper bound of the two-sided 95% confidence interval of the hazard ratio of the two treatment arms is below 1.

7.4.3.11 Change from BL to each post-dosing study visit in Total cholesterol, LDL/High-density Lipoprotein (HDL) ratio, Non-HDL cholesterol, Apolipoproteins A1 and B, ApoB/ApoA1 ratio

Descriptive statistics (value, change from baseline) by visit and treatment arm. Descriptive statistics will also be reported regardless of fasting status.

7.4.3.12 Occurrence of mean LDL cholesterol <100 mg/dL calculated over weeks 12 to 28

The number and percentage of subjects with mean LDL cholesterol less than 100 mg/dL (fasting values and regardless fasting status) on average in weeks 12-28 will be reported by treatment arm and by baseline value.

7.4.3.13 Occurrence of achieved antihypertensive treatment goal in CKD subjects (SBP < 130 mmHg and DBP < 80 mmHg) based on the mean SBP and mean DBP calculated over weeks 12 to 28.

The number and percentage of subjects with achieved antihypertensive treatment goal over an evaluation period defined as the average of available values in weeks 12-28 will be reported by treatment arm.

7.4.3.14 Health related Quality of Life Questionnaires Change from BL to the average value of weeks 12 to 28

The following questionnaires will be analyzed:

- SF-36 (Physical Component Score (PCS));
- FACT-An (Anemia Subscale (“Additional Concerns”), Total FACT-An Score);
- EQ-5D 5L (VAS Score);
- Work Productivity and Activity Impairment Questionnaire: Anemic Symptoms (WPAI:ANS).

SF-36 and FACT-An

Descriptive statistics (value, change from baseline) will be presented for SF-36 (subscale and component scores) and FACT-An (total and subscale scores) by visit and treatment arm. Mean values will also be plotted over time and by treatment arm.

In addition, for the average value in weeks 12-28, an inferential analysis, similar to the one defined in Section [7.4.2.1](#) will be performed for the following endpoints:

- Physical Component Scores of SF-36 (SF-36 PCS)
- Anemia Subscale (“Additional Concerns”) of FACT-An Scores
- Total FACT-An Scores

For SF-36, at each visit, the frequency and proportion of subjects with a change from baseline ≤ 3 points and ≤ 5 points will be reported for Physical Functioning, Vitality and Physical Component scores.

EQ-5D 5L

For the EQ-5D 5L VAS score, change from baseline to each visit and to the average of weeks 12-28 will be described by treatment arm.

For the 5 EQ-5D 5L qualitative domains, the number and percentage of subjects in each response level value will be reported by visit and treatment arm.

Work Productivity and Activity Impairment (WPAI)

The number and proportion of employed subjects will be reported by visit and treatment arm.

WPAI calculated variables will be summarized descriptively by visit and treatment arm.

Furthermore, change from baseline to each visit and to the average of weeks 12-28 and 36-52 will be described by treatment arm.

7.4.3.15 Patients’ Global Impression of Change (PGIC)

Patients’ Global Impression of Change will be summarized descriptively by visit and treatment arm.

7.4.3.16 Heparin and Iron, HbA1c and CKD progression parameters

Changes from baseline to each study visit will be calculated for these parameters:

- Serum hepcidin
- Serum ferritin
- TSAT
- HbA1c level
- Fasting blood glucose
- Serum creatinine (log transformed)
- Albumin/creatinine ratio in urine (log-transformed)

Descriptive statistics and frequency tabulations will be presented for these parameters and for the change from baseline by visit and treatment arm. Mean values will also be plotted versus visit by treatment arm.

Geometric Mean (GM) and coefficient of variation (CV) will be displayed for serum creatinine and albumin/creatinine ratio in urine. In addition, GM Ratio from baseline and 95% CI will be presented these parameters by transforming the change from baseline of the log-transformed data back to the original scale.

All time to event endpoints as defined in Section [6.1.3.16](#) will be analyzed using the same methods described in Section [7.4.2.7](#) on the FAS. Superiority will be declared if the lower bound of the two-sided 95% confidence interval of the hazard ratio is above 1.

As a sensitivity analysis, the above stratified cox model will be repeated using IPCW method (Appendix [10.7](#)) for the following endpoints:

- Time to CKD progression (composite of doubling serum creatinine, chronic dialysis or renal transplant, and Death)

If the conclusions of the analysis using stratified cox model and IPCW method are not concordant, additional analysis using IPCW method will performed for each of the following endpoints separately.

- Time to doubling of serum creatinine
- Time to chronic dialysis or renal transplant
- Time to occurrence for a subject who died or chronic dialysis or renal transplant
- Time to at least 40% decrease in eGFR from baseline, chronic dialysis or renal transplant

If the conclusions of the analysis using stratified cox model and IPCW method are not concordant, additional analysis using IPCW method will performed for each of the following endpoint separately.

- Time to at least 40% decrease in eGFR from baseline

A listing of dialysis data will also be provided.

7.4.4 Analysis of Exploratory Variables: hs-CRP (High Sensitivity C-Reactive Protein) and sTFR (Soluble Transferrin Receptor)

For each visit, descriptive statistics with the absolute values and change from baseline for hs-CRP and sTFR will be displayed by treatment arm.

Genotyping will be shipped to a delegated CRO and analyzed under the responsibility of Bioanalysis-Europe of Astellas Pharma Europe B.V. A separate report will be provided.

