4. TSAT
5. HbA1c level
6. Fasting blood glucose
7. Serum creatinine (log transformed)
8. Albumin/creatinine ratio in urine (log transformed)

Serum creatinine and albumin/creatinine ratio in urine will be log transformed and any assessment occurring after the initiation of any dialysis (acute or chronic) will be excluded for the summaries.

For all variables above, baseline assessment is the assessment from Day 1 visit. If this value is missing, then the screening period value, if collected for that parameter, will be used.

CKD Progression variables:

- Time to CKD progression (composite of doubling serum creatinine, chronic dialysis or renal transplant, and Death)

First occurrence of serum creatinine being doubled compared with baseline during the Safety Emergent Period (see Section 6.2) will be calculated.

Occurrence of chronic dialysis or renal transplant (whichever occurring first) during the Safety Emergent Period (see Section 6.2) will be calculated.

Time to occurrence for a subject who died during the Safety Emergent Period (see Section 6.2) will be calculated.

For a subject, the time to CKD progression will be calculated (in years) as:

$$(\text{First event date} - \text{Analysis date of first dose intake} + 1) / 365.25$$

With 'First event date' defined as 'First occurrence of serum creatinine being doubled compared with baseline, first occurrence of chronic dialysis or renal transplant, occurrence of subject who died (whichever occurring first)' and 'Analysis date of first dose intake' defined in Section 6.5.4

For a subject without event, the time to censoring will be calculated (in years) as:

$$(\text{End of Safety Emergent Period} - \text{Analysis date of first dose intake} + 1) / 365.25$$

With 'Analysis date of first dose intake' defined in Section 6.5.4

- Time to chronic dialysis or renal transplant or occurrence for a subject who died Occurrence of chronic dialysis or renal transplant (whichever occurring first) during the Safety Emergent Period (see Section 6.2) will be calculated.

Time to occurrence for a subject who died during the Safety Emergent Period (see Section 6.2) will be calculated.

For a subject, the time to chronic dialysis or renal transplant or occurrence for a subject who died will be calculated (in years) as:

$$(\text{First event date} - \text{Analysis date of first dose intake} + 1) / 365.25$$

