7 STATISTICAL METHODOLOGY

7.1 General Considerations

- All statistical comparisons will be made using two sided tests at the $\alpha=0.05$ significance level unless specifically stated otherwise. Null hypotheses for superiority testing will be of no treatment difference and corresponding alternative hypothesis will be two-sided. Null hypotheses for non-inferiority testing will be of inferiority of roxadustat treatment and will be one-sided at the $\alpha=0.025$.
- All data processing, summarization, and analyses will be performed using SAS® Version 9.3 (SAS Enterprise Guide 4.3) or higher. Specifications for tables, data listings and figures (TLFs) formats can be found in the TLF Specifications for this study.
- All data will be summarized by treatment arm (roxadustat and placebo) and for the total, unless specified otherwise.
- For continuous variables that are recorded as “< X” or “> X”, the value of “X” will be used in the calculation of summary statistics. The original values will be used for the listings.
- All percentages will be rounded to one decimal place and lined up by the decimal place. The percentage will be suppressed when the count is zero.
- Any p-values will be rounded to four decimal places and will be presented as ‘< 0.0001’ if they are less than 0.0001 after rounding.
- For continuous variables, descriptive statistics will include the number of subjects (n), mean, standard deviation, median, minimum and maximum. Frequencies and percentages will be displayed for categorical data. Percentages by categories will be based on the number of subjects with no missing data, i.e., will add up to 100%. Number of missing values will be shown in the frequencies tables
- All data included in summary tables, inferential analyses or figures will also be listed.
- Listings will be done on all randomized subjects and all assessments (all collected data in the eCRF will be listed except the physical examination data).
- Model checking will be performed using graphical outputs provided by the SAS procedures.

For the definition of subgroups of interest please refer to Section [7.8](#).

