Non-inferiority will be declared if the upper bound of the 2-sided 95% confidence interval of the hazard ratio (roxadustat as relative to placebo), calculated on the PPS, is below 1.3. As per [Table 16](#), once the null hypothesis is rejected, superiority will be checked for this variable on the FAS, as part of the fixed sequence testing procedure. Superiority will be concluded if the upper bound of the two-sided 95% CI of the hazard ratio of the two treatment arms (roxadustat as relative to placebo) is below 1.

The stratified Cox Model can be written:

$$\lambda_j(t; \underline{x}) = \lambda_{0j}(t) \exp(\alpha z)$$

where

j - indicator for stratum

z – treatment indicator – which is either roxadustat or placebo

The SAS procedure for the Cox regression will be similar to the following:

```
proc phreg;
  model time_to_event*cens_var(1) = treatment Hb_Bas eGFR_bas / rl;
  strata CVHist Region;
run;
```

The SAS procedure for the Cox regression using IPCW method uses above similar code with weight statement. Refer to Appendix 10.7 for details.

Table 23 Primary and sensitivity analysis for the time to first occurrence of hypertension

Code	Set	Endpoint	Method	Stratas/Covariates
Primary	PPS	time to first occurrence of hypertension	Cox regression + Kaplan Meier	Stratified on Region and History of CV, and adjusted on BL Hb, BL eGFR as continuous covariates
S1	All Randomized	time to first occurrence of hypertension	Cox regression + Kaplan Meier	Stratified on Region, History of CV and adjusted on BL Hb, BL eGFR as continuous covariates
S2	FAS	time to first occurrence of hypertension	Cox regression + Kaplan Meier	Stratified on Region, History of CV and adjusted on BL Hb, BL eGFR as continuous covariates

In addition, the cumulative incidence curve of subjects with an increase in blood pressure from baseline will be plotted by treatment arm.

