7.4.3 Analysis of Additional Secondary Efficacy Endpoints

All the analyses below will be superiority tests. These inferential analyses will be performed on the FAS and presented treatment effect as Roxadustat versus placebo.

Descriptive statistics will be presented by treatment arm.

7.4.3.1 Hb level averaged over weeks 28 to 36, 44 to 52, and 96 to 104 without use of rescue therapy within 6 weeks prior to and during these 8-week evaluation periods

Averaged Hb over weeks 28-36, 44 to 52 and 96 to 104 will be described by treatment arm on the FAS.

The SAS procedure will be similar to the one provided in Section 7.4.2.1

In addition, the number and proportion of subjects with average Hb over weeks 28-36 and over weeks 44-52 and 96-104 and by visit within the <10 g/dL, 10-12 g/dL and >12 g/dL categories will be reported.

7.4.3.2 Time to achieve the first Hb response as defined by primary endpoint for EU (EMA)

Time to achieve the first Hb response, without rescue therapy, will be analyzed using the same methods described in Section 7.4.2.7 on the FAS.

Superiority will be declared if the lower bound of the two-sided 95% confidence interval of the hazard ratio is above 1.

Cumulative incidence will be provided at 4, 8, 16, and 24 weeks with their associated 95% confidence interval reported using Greenwood's formula.

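### SAP 7.4.3.16 reverses the superiority rule for the CKD-progression time-to-event endpoints, so significantly more renal events on roxadustat would be declared superiority

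*SAP*

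**What the plan says.** SAP 7.4.3.16 takes every time-to-event endpoint of SAP 6.1.3.16 together. They "will be analyzed using the same methods described in Section" 7.4.2.7, on the FAS, and the decision rule follows at once: "Superiority will be declared if the lower bound of the two-sided 95% confidence interval of the hazard ratio is above 1".

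Three other places fix what that rule means.

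- **Direction of the ratio.** SAP 7.4.2.7 concludes superiority when the upper bound for the "hazard ratio of the two treatment arms (roxadustat as relative to placebo) is below 1". The opening of SAP 7.4.3 says of the whole section that "All the analyses below will be superiority tests", with inferential analyses that "presented treatment effect as Roxadustat versus placebo".
- **Type of event.** SAP 6.1.3.16 begins its list with "Time to CKD progression (composite of doubling serum creatinine, chronic dialysis or renal transplant, and Death" and continues with narrower renal endpoints and ESRD-free survival.
- **Rule for other unwanted events.** For first hospitalization, SAP 7.4.3.6 requires that the "upper bound of the two-sided 95% confidence interval of the hazard ratio of the two treatment arms is below 1".

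**The concern.** When the ratio is roxadustat over placebo and the event is bad, benefit lies below 1. A rule that needs the interval to lie entirely above 1 attaches the word superiority to significant harm and withholds it from significant benefit.

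The endpoints are renal outcomes, some of them including death, in patients with stage 3 to 5 CKD. A prespecified criterion for them should not work only because the reader ignores what it says. Reversing it after unblinding would be a post hoc change to a decision rule, even if an obvious one.

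**Working it through.** **No figure to reproduce.** The SAP gives no power, event count or target hazard ratio for these endpoints. The check is logical, followed by an illustration.

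**Step 1: direction of the hazard ratio.** Roxadustat relative to placebo (SAP 7.4.2.7; the opening of 7.4.3 agrees). A ratio above 1 means a higher event rate on roxadustat. Nothing in either document inverts the ratio for the CKD endpoints.

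**Step 2: the events (SAP 6.1.3.16).**

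| Endpoint | Event counted |
|---|---|
| CKD progression | creatinine doubling, chronic dialysis or transplant, death |
| Dialysis, transplant or death | chronic dialysis or transplant, death |
| Creatinine doubling | doubling from baseline |
| Doubling, dialysis or transplant | whichever is first |
| Dialysis or transplant | whichever is first |
| ESRD-free survival | ESRD or death |
| 40% eGFR decrease, dialysis or transplant | whichever is first |
| 40% eGFR decrease | first fall of at least 40% |

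All eight are unfavourable. ESRD-free survival is no exception: despite its name, the modelled event is ESRD or death.

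**Step 3: the SAP's superiority rules side by side.**

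| Section | Event | Rule for superiority | Direction |
|---|---|---|---|
| 7.4.2.3 | rescue therapy | upper bound below 1 | right |
| 7.4.2.7 | hypertension | upper bound below 1 | right |
| 7.4.3.6 | hospitalization | upper bound below 1 | right |
| 7.4.3.7 to 7.4.3.10 | rescue in first 24 weeks, RBC transfusion, IV iron, ESA | upper bound below 1 | right |
| 7.4.3.2 | Hb response (wanted) | lower bound above 1 | right |
| 7.4.3.16 | CKD progression (unwanted) | lower bound above 1 | reversed |

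The sentence in 7.4.3.16 is the same as the one in 7.4.3.2, where it is correct because Hb response is the desired outcome. That suggests a copying slip, though the SAP does not say so.

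Two example intervals show the effect. An interval of 0.55 to 0.90 (benefit) is not superior as written. An interval of 1.10 to 1.80 (harm) is.

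**Step 4: illustration.** Inputs: 2:1 allocation (SAP 4); two-sided 95% interval; number of events D assumed. With the usual normal approximation for the log hazard ratio,

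se = 1/√(D × 2/3 × 1/3) = 1/√(2D/9)

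P(lower bound > 1) = Φ(ln HR/se − 1.96)

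P(upper bound < 1) = Φ(−ln HR/se − 1.96)

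At D = 150, se = 1/√33.33 = 0.1732.

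- True HR 1.5: ln 1.5 = 0.405, and 0.405/0.1732 = 2.34. The written rule fires with probability Φ(2.34 − 1.96) = Φ(0.38) = 65%. The same calculation gives 32% at D = 60 and 77% at D = 200.
- True HR 0.6: ln 0.6 = −0.511, and −0.511/0.1732 = −2.95. The written rule fires with probability Φ(−4.91), about 0. The rule in the right direction fires with probability Φ(0.99) = 84%.

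For a smaller benefit, true HR 0.70:

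| Events assumed | Rule as written | Upper bound below 1 | Observed HR needed, as written | Observed HR needed, right direction |
|---|---|---|---|---|
| 50 | 0.08% | 22% | above 1.80 | below 0.56 |
| 100 | 0.01% | 39% | above 1.52 | below 0.66 |
| 150 | 0.003% | 54% | above 1.40 | below 0.71 |
| 200 | 0.001% | 66% | above 1.34 | below 0.75 |

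At HR = 1 each rule fires 2.5% of the time, so the correction leaves the one-tail error rate unchanged.

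**The case against.** The strongest reply is that the SAP corrects itself. The sentence before the disputed one adopts the methods of 7.4.2.7, and 7.4.2.7 contains the superiority rule in the right direction. It is fair to call this an internal contradiction. It does not remove the problem, because a general reference to methods does not override an explicit decision rule stated immediately after it for these endpoints.

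Other points stand but bear on priority, not on correctness:

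- These are additional secondary endpoints, outside the Table 16 sequence. The renal endpoint among the key secondaries, eGFR slope (SAP 7.4.2.8), has its rule the right way round.
- Death is not a stand-alone endpoint in 6.1.3.16; it enters through composites and ESRD-free survival. Mortality is analysed separately under safety (SAP 7.5.1.4), with no superiority rule attached.
- The hazard ratio and its interval would be reported in any case, and SAP 7.1 makes tests two-sided at 0.05. A significant benefit would be visible; only the formal declaration would be wrong.
- The percentages rest on assumed event counts, with one count applied to endpoints whose event rates will differ.

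There is also one knock-on effect. SAP 7.4.3.16 triggers further IPCW analyses when the Cox and IPCW conclusions disagree, so a misdirected definition of the conclusion could affect that trigger. The consequence would be limited to which sensitivity analyses are run.

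**Conclusion.** The concern holds. As written, superiority on the CKD-progression endpoints is declared only when the estimated hazard of an unfavourable event is significantly higher on roxadustat. This follows from the ratio's direction and the nature of the events and needs no assumption about event numbers.

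The size does need one. With 2:1 allocation and 60 to 200 events, a true hazard ratio of 1.5 would be called superiority 32% to 77% of the time. At 150 events, a true ratio of 0.6 would almost never be, against 84% under the correct rule. The primary and key secondary conclusions are not touched. It must still be corrected, because the rule is wrong on its face and governs renal and death-containing composites.

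**What to change.** Replace the decision sentence in SAP 7.4.3.16 with wording to this effect:

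*Superiority is concluded when the upper limit of the two-sided 95% CI for the hazard ratio (roxadustat relative to placebo) lies below 1.*

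Leave SAP 7.4.3.2 as it is, since the other direction is right for time to Hb response.

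The cost is one sentence, with no change to data, model, analysis set or sample size. SAP section 1 allows version-controlled revision up to database hard lock, and the change belongs there. If lock has passed, section 1 requires the departure to be justified in the clinical study report.
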